6.6.9. MUGA/ECHO

LVEF% will be summarized using simple descriptive statistics (mean, SD, median, Q1, Q3, minimum, and maximum) of actual values and changes from baseline for each nominal visit over time. In addition, LVEF% will be summarized as frequency (number and percentage) of patients with:

- a shift from baseline normal to at least one result below the institutional lower limit of normal during the on-treatment period
- ≥ 10 -point decrease from baseline in LVEF% during the on-treatment period
- ≥ 10 -point decrease from baseline in LVEF% to a post-baseline value $< \text{LLN}$ during the on-treatment period
- ≥ 15 -point decrease from baseline in LVEF% during the on-treatment period
- ≥ 15 -point decrease from baseline in LVEF% to a post-baseline value $< \text{LLN}$ during the on-treatment period.

Clinically significant findings will be listed.

6.6.10. Electrocardiogram

ECG summaries will include all ECG assessments from the on-treatment period. All ECG assessments will be listed, and those collected outside the on-treatment period will be flagged in the listing. QTcB and QTcF will be derived based on RR and QT (see below). The average of the replicate measurements should be determined after the derivation of the individual parameter at each time point.

Selecting Primary QT Correction for Heart Rate

The analysis of QT data is complicated by the fact that the QT interval is highly correlated with heart rate. Because of this correlation, formulas are routinely used to obtain a corrected value, denoted QTc, which is independent of heart rate. This QTc interval is intended to represent the QT interval at a standardized heart rate. Several correction formulas have been proposed in the literature. For this analysis we will use some of those methods of correction, as described below. The QT interval corrected for heart rate by the Bazett's formula, QTcB, is defined as

$$QTcB = \frac{QT}{\sqrt{RR}},$$

the QT interval corrected for heart rate by the Fridericia's formula, QTcF, is defined as

$$QTcF = \frac{QT}{\sqrt[3]{RR}},$$

where RR represents the RR interval of the ECG, in seconds, and can be estimated as 60/Heart Rate.

Although Bazett's correction is the historical standard, it does not perform well when heart rate fluctuates. Fridericia's formula may perform better under these conditions. If QTcB and QTcF methods do not adequately correct for HR and there are a sufficient number of patients (e.g. >30) with baseline ECGs, an alternate correction to achieve the goal of getting uncorrelated QTc and RR is based on a linear regression methods which yields, theoretically, uncorrelated QTc and RR.

Linear regression method:

- Fit a model $QT = a + b \times RR$ to baseline data
- Use the estimated slope, \hat{b} , to correct QT
- Corrected QT for heart rate will be computed as follows:

$$QTcP = QT + \hat{b} \times (1 - RR)$$

Data will be summarized using QTcF and QTcB. However, if these are not appropriate for the data set due to an observed large correlation between corrected QT and HR using the baseline assessments, the results will also be summarized using QTcP.

ECG Summaries

The following analyses will be performed for each applicable ECG parameters (RR, PR, QRS, QT, ventricular rate -denoted as HR in what follows-, and QTc) by treatment arm, during the on-treatment period. The denominator to calculate percentages for each category is the number of patients evaluable for the category.

- Pearson correlation between QT and HR, QTc (QTcB, QTcF and, if applicable, QTcP) and HR using individual (non-averaged) baseline assessments
- For each of the ECG parameters (HR, and QT, QTc, QRS, PR intervals), descriptive statistics at baseline, at each post-baseline time point and changes from baseline at each post-baseline time point
- Frequency (number and percentage) of patients with notable ECG values according to the following categories:
 - QT/QTc increase from baseline >30 ms, >60 ms
 - QT/QTc > 450 ms, > 480 ms, > 500 ms
 - HR ≤ 50 bpm and decrease from baseline ≥ 20 bpm
 - HR ≥ 120 bpm and increase from baseline ≥ 20 bpm
 - PR ≥ 220 ms and increase from baseline ≥ 20 ms
 - QRS ≥ 120 ms

Patients with notable ECG interval values and qualitative ECG abnormalities will be listed for each patient and time point and the corresponding notable values and abnormality findings will be included in the listings.

Unscheduled ECG measurements will not be used in computing the descriptive statistics for change from baseline at each post-baseline time point. However, they will be used in the analysis of notable ECG changes and the shift table analysis of notable QT parameters.

6.6.11. Physical examination

Number and percentage of patients with abnormal findings in physical examination will be summarized by body system.

6.6.12. ECOG performance status

The ECOG shift from baseline to highest score during the on-treatment period will be summarized by treatment arm. ECOG performance status with shift from ECOG=0 or 1 to ECOG 2 or higher will also be presented in a data listing.

7. INTERIM ANALYSES

7.1. Introduction

The interim analyses will be performed by an independent statistician. The goals of the interim analyses are to allow early stopping of the study for futility or efficacy. The interim analysis of PFS and OS will be performed as described in Sections 5.1.1 and 5.1.2 using the methodology described in Section 6.1.1 for PFS and Section 6.1.2 for OS.

At the time of the interim analysis for PFS in PD-L1 positive patients, the first interim analysis for OS in PD-L1 positive patients will be performed.

If the interim analysis for PFS in PD-L1 positive patients crosses the pre-specified boundary for efficacy, the interim analysis for PFS for patients unselected for PD-L1 expression will be performed at the same time. If the interim analysis for PFS for patients unselected for PD-L1 expression or the first interim analysis for OS in PD-L1 positive patients cross the pre-specified boundaries for efficacy, then the first interim analysis for OS for patients unselected for PD-L1 expression will be performed at the same time.

Unblinded results from the interim analyses will not be communicated to the Sponsor's clinical team or to any party involved in the study conduct (apart from the independent statistician and E-DMC members) until the E-DMC has determined that either (i) PFS in PD-L1 positive patients analysis has crossed the pre-specified boundary for efficacy or (ii) OS in PD-L1 positive patients analysis has crossed the pre-specified boundary for efficacy or (iii) the study needs to be terminated due to any cause, including futility or safety reasons. Further details will be described in the E-DMC charter.

At the time of final analysis for PFS in PD-L1 positive patients, the second interim analysis for OS in PD-L1 positive patients will be performed. If the final analysis for PFS in PD-L1 positive patients crosses the pre-specified boundary for efficacy, the final analysis for PFS in

patients unselected for PD-L1 expression will be performed at the same time. If the final analysis for PFS in patients unselected for PD-L1 expression or the second interim analysis for OS in PD-L1 positive patients cross the pre-specified boundaries for efficacy, then the second interim analysis for OS for patients unselected for PD-L1 expression will be performed at the same time.

The third interim analysis for OS in PD-L1 positive patients will be performed 15 months after the final analysis for PFS. If the third interim analysis for OS in PD-L1 positive patients crosses the pre-specified boundary for efficacy, the third interim analysis for OS for patients unselected for PD-L1 expression will be performed at the same time.

All patients will continue to be followed for OS until the final OS analysis (or earlier if OS in patients unselected for PD-L1 expression reaches statistical significance at an interim analysis).

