## 6.4. End of the Study

The study will end when at least 368 OS events in the PD-L1+ population (patient population prospectively defined as noted in [Section 7.5.1](#)) have occurred.

At the end of study, Arm A patients who are still deriving clinical benefit from study treatment will be provided with an option for continued study treatment (eg, rollover study).

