If  $H_{01}$  is rejected then PFS in the 'all comers' population can be tested and 490 PFS event by BICR assessment will provide 90% power to detect a HR of 0.70 using a 1-sided log rank test at a significance level of 0.004, and a 2-look group sequential design with Lan-DeMets (O'Brien-Fleming)  $\alpha$ -spending function to determine the efficacy boundary.

If either  $H_{02}$  or  $H_{03}$  are rejected, then OS in the 'all comers' population can be tested at the sum of the significance levels associated with the significant  $H_{02}$  and  $H_{03}$  tests (see Figure 2). With 534 OS events, the power is 91% (if both  $H_{02}$  and  $H_{03}$  are rejected), 90% (if  $H_{02}$  is rejected and  $H_{03}$  is not rejected) or 74% (if  $H_{02}$  is not rejected and  $H_{03}$  is rejected) to detect a HR of 0.75 using a 1-sided log rank test at a significance level of 0.025, 0.021 or 0.004, respectively, and a 4-look group sequential design with Lan-DeMets (O'Brien-Fleming)  $\alpha$ -spending function to determine the efficacy boundary.

The data cutoff for the primary PFS analysis will occur after the target number of PFS events by BICR assessment in the PD-L1+ population has been reached and the last patient randomized in the study has been followed for at least 12 months after randomization.

The data cutoff for the primary OS analysis will occur after the target number of deaths in the PD-L1+ population has been reached.

The study will be considered positive if the stratified log-rank test for either PFS or OS in the PD-L1+ population is significant at the respective  $\alpha$  levels.

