The sample size for this study is determined based on the following:

1. the median PFS for patients receiving sunitinib is 11 months (Sutent Summary of Product Characteristics) and the median PFS for patients receiving avelumab in combination with axitinib is 16.9 months for PD-L1 positive patients and 15.7 months for patients unselected for PD-L1 expression; this, corresponds to a hazard ratio (HR) of 0.65 and 0.7, respectively under the exponential model assumption;
2. the median OS for patients receiving sunitinib is 26.4 months (Sutent Summary of Product Characteristics) and the median OS for patients receiving avelumab in combination with axitinib is 37.7 months for PDL1 positive patients and 35.2 months for patients unselected for PD-L1 expression; this corresponds to a HR of 0.7 and 0.75, respectively under the exponential model assumption;

3. PFS drop-out rate of approximately 15% and OS drop-out rate of approximately 5%;
4. 70% of the randomized patients are PD-L1 positive;
5. non-uniform patient accrual accomplished over a 21 month period.

The sample size of approximately 830 patients will also allow an assessment of PFS and OS in patients unselected for PD-L1 expression.

If H_{01} is rejected then PFS in patients unselected for PD-L1 expression can be tested and 490 PFS events by BICR assessment will be required to have at least 90% power to detect a HR of 0.70 using a 1-sided log rank test at a significance level of 0.004, and a 2-look group sequential design with Lan-DeMets (O'Brien-Fleming) α -spending function to determine the efficacy boundary.

If either H_{02} or H_{03} are rejected, then OS in patients unselected for PD-L1 expression can be tested at the sum of the significance levels associated with the significant H_{02} and H_{03} tests (see Figure 1). With 534 OS events, the power is 91% (if both H_{02} and H_{03} are rejected), 90% (if H_{02} is rejected and H_{03} is not rejected) or 74% (if H_{02} is not rejected and H_{03} is rejected) to detect a HR of 0.75 using a 1-sided log rank test at a significance level of 0.025, 0.021 or 0.004, respectively, and a 4-look group sequential design with Lan-DeMets (O'Brien-Fleming) α -spending function to determine the efficacy boundary.

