7.2.4. Interim analysis for OS in patients unselected for PD-L1 expression

Throughout this section, references to OS pertain to OS in patients unselected for PD-L1 expression.

The interim analysis for OS for patients unselected for PD-L1 expression will be performed according to the testing strategy described in Section 7.1 and in Section 5.1.1. No futility analysis will be performed for OS for patients unselected for PD-L1 expression.

Let $u(t_i)$ and $u(t_F)$ denote the upper critical boundaries based on the test statistics Z_i and Z_F for efficacy at the i^{th} interim and the final analysis, respectively, where $i=1, 2, 3$.

In what follows P_0 denote the probability under the null hypothesis and $\alpha(t_i)$ denote the α spent based on the predefined spending functions at information fraction t_i (t_i is calculated as the ratio of the number of OS events observed at the time of the cut-off for the i^{th} interim analysis and the total number of OS events targeted for the final analysis).

The critical value $u(t_1)$ for the 1st interim analysis of OS are determined such as

$$P_0(Z_1 \geq u(t_1)) = \alpha(t_1) ,$$

Critical boundaries for the additional interim analyses and the final analysis of OS are calculated recursively as follows

$$u(t_2) \text{ is derived such that } \alpha(t_1) + P_0(Z_1 < u(t_1), Z_2 \geq u(t_2)) = \alpha(t_2) ,$$

$$u(t_3) \text{ is derived such that } \alpha(t_2) + P_0(Z_1 < u(t_1), Z_2 < u(t_2), Z_3 \geq u(t_3)) = \alpha(t_3)$$

The boundary for the final efficacy analysis is derived such that

$$\alpha(t_3) + P_0(Z_1 < u(t_1), Z_2 < u(t_2), Z_3 < u(t_3), Z_F \geq u_F) = \alpha'$$

where $\alpha' = 0.025$ or 0.021 or 0.004 for the analysis of OS in patients unselected for PD-L1 expression as determined according to the testing strategy described in Section 5.1.1.

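### SAP 7.1 names only PD-L1+ OS as the IA3 trigger for testing all-comers OS, against SAP 5.1.1, and lets OS follow-up end with the primary PD-L1+ OS test still open, against Protocol 6.4

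*SAP*

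**What the plan says.** Four hypotheses matter here: H01 (PFS, PD-L1+), H02 (OS, PD-L1+), H03 (PFS, all comers) and H04 (OS, all comers). H01 and H02 are primary.

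- **Gatekeeping rule.** SAP 5.1.1: "If either H_{02} or H_{03} are rejected, then OS in patients unselected for PD-L1 expression can be tested". Protocol 9.1 has the same rule: the all-comers "population can be tested at the sum of the significance levels associated with the significant" tests. Neither limits the rule to particular looks.
- **IA1 and IA2.** SAP 7.1 names both routes. At IA2: "If the final analysis for PFS in patients unselected for PD-L1 expression or the second interim analysis for OS in PD-L1 positive patients cross" their boundaries, all-comers OS is tested at that look. The IA1 sentence has the same form.
- **IA3.** SAP 7.1 names one route: "If the third interim analysis for OS in PD-L1 positive patients crosses the pre-specified boundary for efficacy".
- **Boundaries.** SAP 7.2.4 says the H04 interim analysis "will be performed according to the testing strategy described in Section 7.1 and in Section 5.1.1". It defines boundaries for all three interims, with total alpha 0.025 "or 0.021 or 0.004 for the analysis of OS in patients unselected for PD-L1 expression as determined according to the testing strategy".
- **Follow-up.** SAP 7.1 follows patients for OS to the final OS analysis, "or earlier if OS in patients unselected for PD-L1 expression reaches statistical significance at an interim analysis". Protocol 6.4 has one criterion: "The study will end when at least 368 OS events in the PD-L1+ population" have occurred.

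**The concern.** PFS testing is finished before IA3, so an H03 win can open H04 at IA3 only if it carries forward. SAP 7.1 never says that a rejection carries forward. At IA2 the PFS trigger it names is the final PFS analysis, which leaves a rejection at the PFS interim unaddressed. Section 7.2.4 then sends the independent statistician to two sections that differ.

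The case affected is a plausible one: PFS won in both populations, PD-L1+ OS not yet won. The choice between the two readings would be made after unblinded data exist.

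The follow-up clause is a separate problem. H04 is secondary. Through H03 it can be won at alpha 0.004 at IA1 or IA2 under 7.1 as written. The clause has no condition on H02, so a secondary result could end data collection for a primary hypothesis that holds 0.021 of the 0.025 alpha.

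**Working it through.** **Inputs.** Planned deaths at IA1, IA2, IA3 and final: PD-L1+ 125, 195, 294, 368 (SAP Table 5); all comers 182, 283, 427, 534 (SAP Table 6). Design hazard ratios for OS: 0.70 in PD-L1+ and 0.75 in all comers (SAP 5.1.1). Allocation 1:1. H02 alpha 0.021; H04 alpha 0.025, 0.021 or 0.004.

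**Formulas.** Mean of the log-rank statistic at look k: −ln(HR) × √(D_k/4). Lan-DeMets O'Brien-Fleming spending: α(t) = 2[1 − Φ(z_{1−α/2}/√t)].

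**Reproducing the plan's figures.**
- H02 boundaries at 0.021: 3.7913, 2.9686, 2.3524, 2.0975, as in Table 5.
- H04 boundaries at 0.025: 3.6656, 2.8726, 2.2727, 2.0286, as in Table 6.
- H04 power for HR 0.75, four looks, at 0.025 / 0.021 / 0.004: 90.8% / 89.6% / 74.3%, against 91% / 90% / 74% stated.

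**The H03-only route (alpha 0.004).** Boundaries are 4.793, 3.786, 3.021, 2.688. At IA3 the mean statistic is 0.2877 × √(427/4) = 2.97. Cumulative power is 0.2%, 8.6%, 48.2%, 74.3%. With IA3 never taken and the other boundaries unchanged, final power is 73.8%. Most of the 39.6-point gain at IA3 is not exposed to the wording, because H02 usually crosses by then too; the joint calculation below isolates what is.

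**Joint behaviour of H02 and H04.** I simulated the two OS score processes with PD-L1+ nested in all comers and independent increments (1 to 2 million trials per scenario). H03 is taken as rejected from IA1 on. Only the first hazard-ratio pair comes from the documents; the other three are illustrative. The PD-L1-negative HR follows by weighting by deaths, for example exp[(534 ln 0.75 − 368 ln 0.70)/166] = 0.87.

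| HR PD-L1+ / all comers | Implied HR PD-L1− | H04 first crosses at IA3, H02 open | Of these, H04 still won at final | Follow-up could end with H02 open, 7.1 as written (IA1–IA2) | Of these, H02 would later be rejected | Follow-up could end with H02 open, IA3 trigger corrected only |
|---|---|---|---|---|---|---|
| 0.70 / 0.75 (design) | 0.87 | 1.0% | 97% | 0.4% | 99% | 1.4% |
| 0.75 / 0.75 | 0.75 | 6.2% | 98% | 1.7% | 95% | 7.9% |
| 0.70 / 0.70 | 0.70 | 6.4% | 99% | 3.8% | 98% | 10.2% |
| 0.80 / 0.75 | 0.65 | 17% | 98% | 3.9% | 87% | 21% |

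At the design hazard ratios H02 is still open after IA3 in 23.8% of trials. SAP Table 8 implies 1 − 0.7495 = 25%.

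**Cost of a skipped IA3 look.** At the design hazard ratios about 1.0% × (1 − 0.97) = 0.03% of trials lose the H04 rejection altogether. In the rest the result moves from IA3 to the final analysis, which Table 8 places at months 46 and 61 under the OS alternative: 15 months.

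**Carry-forward.** At the design hazard ratios H02 is won by IA2 with H04 still open in 8.0% of trials. If PD-L1+ OS is recomputed at IA3, the missing carry-forward changes the IA3 result in only 0.02%.

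**The case against.** The strongest reply is that this is a drafting gap with a governing rule at hand. The IA3 sentence says if, not only if. SAP 7.1 opens by referring to 5.1.1 and 5.1.2. Section 5.1.2 plans up to four OS analyses in both populations, and Table 6 and Protocol Table 10 give all-comers OS an IA3 column with no condition on PD-L1+ OS. The testing-strategy figure and the E-DMC charter are not in the text and may settle the matter. All of that is true, so 7.1 does not ban the test. But those passages also show that the design has an IA3 look for which 7.1 gives no H03 trigger. Since 7.1 spells out the PFS route at the two earlier looks, its absence at the third can be read as deliberate.

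On follow-up, Protocol 6.4 is not the only way the study can end: Protocol 9.6 allows a futility stop, 9.7 a recommendation to terminate and 14 termination by the sponsor. That stands, but none of these makes all-comers OS significance a planned end of follow-up.

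On size, the effects at the design hazard ratios are small, and the largest come from a scenario that reverses the premise that PD-L1+ patients benefit more. The figures are also conditional on H03. H03 can be tested only after H01, which SAP Table 7 gives as rejected with probability 0.51 at the interim and 0.89 at the final analysis, so unconditional figures are lower. These points limit the severity. They do not reconcile the texts.

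**Conclusion.** Both parts hold, as an unreconciled conflict and not as a prohibition. SAP 7.1 and 5.1.1 lead to different actions at IA3 when H03 is won and H02 is open. The early-end clause in 7.1 has no counterpart in Protocol 6.4 and can close a primary test on a secondary result.

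The trigger gap affects about 1% of trials under the design assumptions and costs mainly time. The follow-up clause is the rarer problem as written, at 0.4%, but the more serious one, because in 99% of those trials H02 would later have been rejected. Type I error is not inflated, and on the H03 route the study is already positive on PFS. It should be fixed, but it does not threaten the trial's validity.

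The figures assume H03 rejected from IA1, proportional hazards, the planned event counts and no futility stop.

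**What to change.** Change both rules in SAP 7.1 together; correcting the trigger alone raises the chance of ending follow-up with H02 open.

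- **Trigger.** Replace the IA2 and IA3 conditions with one rule that also covers the final analysis: *At IA2, IA3 and the final OS analysis, H04 is tested if H02 or H03 has been rejected at that or any earlier analysis, at the matching level in Section 5.1.1.*
- **Follow-up.** Either delete the early-end clause, which leaves Protocol 6.4 as it is, or restrict it to *earlier only if H02 and H04 have both been rejected* and add the same exception to Protocol 6.4.

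The cost is two or three sentences in the SAP, with no protocol change if the clause is deleted, or one sentence in Protocol 6.4 by amendment if an early end is kept. No test is added beyond what 5.1.1 already allows. The downside is that follow-up runs to 368 PD-L1+ deaths when only H04 has been won, which Protocol 6.4 already requires.

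The protocol's later schedule of activities dates the IA3 cut-off 28 April 2020. If that look has been taken, the trigger edit should record which rule was applied; the follow-up edit still matters until 368 PD-L1+ deaths.

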7.2. Interim Analyses and Summaries

At each analysis time point, the critical boundaries for the group sequential test will be derived from the predefined spending function(s) as described in Section 5.1. The calculations of boundaries will be performed using EAST.

7.2.1. Interim analysis for PFS in PD-L1 positive patients

Throughout this section, references to PFS pertain to PFS by BICR assessment in PD-L1 positive patients.

Let $u(t_1)$ and $u(t_F)$ denote the upper critical boundaries based on the test statistics Z_1 and Z_F for efficacy at the interim and the final analysis, respectively, and let $l(t_1)$ and $l(t_F)$ denote the lower critical boundary for futility at the interim and final analysis, respectively. For the final analysis, $l(t_F)=u(t_F)$.

The critical values $u(t_1)$ and $l(t_1)$ for the interim analysis of PFS are determined such as

$$P_0(Z_1 \geq u(t_1)) = \alpha(t_1) \quad \text{and} \quad P_a(Z_1 \leq l(t_1)) = \beta(t_1) ,$$

where P_0 and P_a denote the probabilities under the null hypothesis and the alternative hypothesis, respectively, and where $\alpha(t_1)$ and $\beta(t_1)$ denote the α and β spent, respectively, based on the predefined spending functions at information fraction t_1 (t_1 is calculated as the ratio of the number of PFS events observed at the time of the cut-off for the interim analysis and the total number of PFS events targeted for the final analysis).

The boundary for the final efficacy analysis will be calculated such that

$$\alpha(t_1) + P_0(Z_1 < u(t_1), Z_F \geq u_F) = 0.004$$

As described in Section 5.1.2, if the number of PFS events in the final analysis deviates from the target number of PFS events, the final analysis criteria will be determined as above taking into account the actual alpha spent at the interim analysis and the actual correlation between

the two test statistics Z_1 and Z_F , so that the overall 1-sided significance level across all analyses and comparisons is preserved at 0.004.

